9.1 Clinical Assessments

9.1.1 Concomitant Medications

All concomitant medications and concurrent therapies will be documented at enrollment, day of procedure, post-operative follow-up visits, and study exit. Dose, unit frequency of administration, and indication for administration and dates of medication will be captured.

9.1.2 Demographics

Demographic information (date of birth, gender, race) will be recorded at enrollment.

9.1.3 Medical History

Relevant medical history, including prior ENT history, cause and size of perforation and length of time present, allergies, other pertinent respiratory history, and information regarding underlying diseases will be recorded at Enrollment.

9.1.4 Physical Examination

A physical examination will be performed by either the investigator or a sub-investigator who is a physician at enrollment. Qualified staff (MD, NP, RN, and PA) may complete an abbreviated physical exam at all other visits. New abnormal physical exam findings must be documented and will be followed by a physician or other qualified staff at the next scheduled visit.

9.1.5 Vital Signs

Body temperature, pulse and respirations will be recorded at each visit. Height and weight will also be obtained.

9.1.6 Otomicroscopy with Photograph of Tympanic Membrane

At each visit otomicroscopy with photograph of tympanic membrane is required.

9.1.7 Adverse Events

Information regarding occurrence of adverse events will be captured from procedure date to study completion. Duration (start and stop dates), severity/grade, outcome, treatment and relation to study device will be recorded on the Adverse Event Tracking Log.

10 EVALUATIONS BY VISIT

Please note that it is acceptable for the Enrollment and Procedure to occur on the same day. Duplicate tasks do not need to be performed and duplicate CRFs are not required to be completed. See section 10.3 for additional information.

10.1 Enrollment / Pre-operative Visit

1. Review the study with the subject (subject's legal guardian) and obtain written informed consent and HIPAA authorization and assent, if appropriate.
2. Assign the subject a unique screening number.
3. Record demographics data.

4. Record general medical history and prior ENT history including the cause and size of perforation and length of time present, allergies, and other pertinent respiratory history.
5. Record concomitant medications.**
6. Perform physical examination, including vital signs.**
7. Otomicroscopy with photograph of tympanic membrane prior to procedure.**
8. Schedule subject for surgical procedure.

10.2 Day of Procedure

1. Concomitant medications review.***
2. Perform abbreviated physical examination.***
3. Perform and record vital signs.***
4. Completion of Procedure and Device Information CRF.
5. Otomicroscopy with photograph of tympanic membrane after procedure with Tympanoseal in place.**
6. If applicable, record any Adverse Events.

**Note: See information below if enrollment and procedure are on the same day.

10.3 If Enrollment and Procedure are on the same day, the following tasks and CRFs are required to be completed.

1. Review the study with the subject (subject's legal guardian) and obtain written informed consent and HIPAA authorization and assent, if appropriate.
2. Assign the subject a unique screening number.
3. Record demographic data. (Enrollment / Demographics CRF)
4. Complete Eligibility Criteria CRF
5. Record general medical history and prior ENT history including the cause and size of perforation and length of time present, allergies, and other pertinent respiratory history. (Medical History (General) and ENT History CRF's)
6. Record concomitant medications. (Concomitant Medication CRF)
7. Perform physical examination, including vital signs. (Pre-Procedure Visit CRF)
8. Otomicroscopy with photograph of tympanic membrane **prior** to procedure.
9. Completion of Procedure and Device Information CRF.
10. Otomicroscopy with photograph of tympanic membrane **after** procedure with Tympanoseal in place.
12. If applicable, record any Adverse Events.

10.4 Follow-up Evaluation - 4 weeks (\pm 7 days)

1. If applicable, record any new Adverse Events.
2. Record changes to concomitant medications.

3. Perform abbreviated physical examination.
4. Perform and record vital signs.
5. Otomicroscopy with photograph of tympanic membrane

Note: If complete healing is noted, then patient may exit the study and Subject Study CRF should be completed.

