4 STUDY DESIGN

This study will be a non-blinded, non-randomized trial. There will be two (2) sites with a limit of fifteen (15) subjects at each site. (Up to thirty (30) total subjects are planned.) Each subject will have Tympanoseal placed during a surgical procedure.

Evaluations will be taken at baseline and up to three evaluations at 4, 10 and 16 weeks. If tympanic healing is noted at any visit, then the subject may exit the study without need for additional follow-up evaluations.

Screening data will be reviewed to determine subject eligibility. Subjects who meet all inclusion criteria and none of the exclusion criteria will be entered into the study. All subjects will be treated with surgically implanted Tympanoseal, either unilaterally or bilaterally as needed.

Total duration of subject participation will be up to 16 weeks post-procedure and total study duration is estimated to be 6 months.

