5 CRITERIA FOR EVALUATION

5.1 Primary Efficacy Endpoint

The primary endpoint will be the healing of the tympanic membrane perforation. In chinchillas this occurred between 1 and 2 months.

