8.1 Blinding / Randomization

This is a non-blinded, non-randomized study.

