10.5 Follow-up Evaluation - 10 weeks (\pm 7 days)

1. If applicable, record any new Adverse Events.
2. Record changes to concomitant medications.
3. Perform abbreviated physical examination.
4. Perform and record vital signs.
5. Otomicroscopy with photograph of tympanic membrane

Note: If complete healing is noted, then patient may exit the study and Subject Study CRF should be completed.

10.6 Follow-up Evaluation - 16 weeks (\pm 14 days) (and additional visits as applicable. See 10.7).

1. If applicable, record any new Adverse Events.
2. Record changes to concomitant medications.
3. Perform abbreviated physical examination.
4. Perform and record vital signs.
5. Otomicroscopy with photograph of tympanic membrane

Note: If complete healing is noted, then patient may exit the study and Subject Study CRF should be completed.

10.7 Potential Additional Follow-Ups at 20 weeks (\pm 14 days), 24 (\pm 14 days), 30 (\pm 14 days), 36 weeks (\pm 14 days) as needed.

It is expected that the Tympanoseal will have resorbed prior to 16 weeks. However, additional visits should be scheduled for 20 weeks, 24 weeks, 30 weeks and 36 weeks until no product remains. The subject may exit the study at any of these intervals after the device is no longer present.

1. If applicable, record any new Adverse Events.
2. Record changes to concomitant medications.
3. Perform abbreviated physical examination.
4. Perform and record vital signs.
5. Otomicroscopy with photograph of tympanic membrane

Note: If complete healing is noted, then patient may exit the study and Subject Study CRF should be completed.

Unscheduled Visit CRF pages will be used to capture 20, 24 and 30 week follow-ups, if needed.

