10.8 Unscheduled Visit(s)

1. If applicable, record any new Adverse Events.
2. Record changes to concomitant medications.
3. Perform complete physical examination, record vital signs, and study evaluations.
4. Otomicroscopy with photograph of tympanic membrane
5. Please note the reason for the visit in the comments section.

Note: If complete healing is noted at this visit, the patient may exit the study and Subject Study CRF should be form completed.

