APPENDIX 1 SCHEDULE OF STUDY VISITS

	Enrollment*	Procedure*	Same Day Enrollment & Procedure	4 Weeks (± 7 days)	10 Weeks (± 7 days)	16 Weeks (± 14 days)	Add'l Visit(s) 20 weeks, 24 weeks, 30 weeks 36 weeks (± 14 days)
Informed Consent	X		X				
Inclusion / Exclusion	X		X				
Medical /ENT History	X		X				
Physical Exam	X*	X*	X	X	X	X	X
Vital Signs	X*	X*	X	X	X	X	X
Study Visit Evaluation	X*	X*	X	X***	X***	X***	X***
Otomicroscopy with Photograph	X**	X**	PRE & POST	X	X	X	X
Use of Study Device		X	X				
Concomitant Medication	X*	X*	X	X	X	X	X
Adverse Event****		X	X	X	X	X	X
Subject Study Exit				X***	X***	X***	X***

*Enrollment and Procedure may be the same visit and duplicate CRFs do not need to be completed. Informed Consent must be signed prior to any study procedures.

** Otomicroscopy with Photograph is required Pre and Post Procedure.

*** If healing is noted by investigator, the subject may exit the study.

**** If applicable

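### One unconfirmed reading of healing is enough for study exit from week 4, so a misread or later reopening in a subject who leaves stays counted as healed

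*Protocol*

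**What the plan says.** Section 5.1 defines the endpoint in one sentence: "The primary endpoint will be the healing of the tympanic membrane perforation". It sets no time point, criterion or confirmation. The only timing it offers is from animals: "In chinchillas this occurred between 1 and 2 months".

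Exit on healing is permitted in several places:

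- Section 4: "If tympanic healing is noted at any visit, then the subject may exit the study without need for additional follow-up evaluations". Section 9 repeats this, and the synopsis allows exit at any follow-up visit where the investigator notes healing.
- The notes to Sections 10.4 to 10.7 (week 4 onward): "If complete healing is noted, then patient may exit the study and Subject Study CRF should be completed".
- Section 10.8, unscheduled visits, with no earliest day: "If complete healing is noted at this visit, the patient may exit the study".
- Appendix 1 names the reader: "If healing is noted by investigator, the subject may exit the study".

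Section 8.1 says of the design: "This is a non-blinded, non-randomized study". Section 9.1.6 requires a photograph at each visit, but no independent or repeat reading is described. Under Section 11.1, adverse events are collected only until the subject exits.

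A subject not read as healed returns at weeks 10 and 16. After that, Section 10.7 adds visits only while device material is visible: "additional visits should be scheduled for 20 weeks, 24 weeks, 30 weeks and 36 weeks until no product remains".

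**The concern.** The two possible readings are treated differently. An ear read as open at week 4 has two more scheduled looks and can become a success. An ear read as closed may have no further look, and if the subject leaves it cannot become a failure. Among those who leave, the endpoint becomes closure seen once, and nobody learns whether the closure was real or lasted.

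Two things are at stake. The first is the healing proportion, which is the named primary endpoint and, under Section 14, goes to the FDA in tabular form. There is no control arm in which the same error would offset it. The second is the safety record, and safety is the primary objective in Section 3.1. Section 2.1 lists incomplete repair or enlargement of the perforation as a risk, yet a reopening after exit is not captured as an adverse event.

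**Working it through.** The protocol states no healing rate, misread rate or reopening rate, so it has no figure of its own to reproduce. The check has one part that rests on the protocol alone and three that rest on stated assumptions.

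**1. Time unobserved after exit at week 4 (protocol only).** Week 4 with its window is day 28 ± 7, that is day 21 to 35. Week 16 is nominally day 112.

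- Exit on day 21: 112 − 21 = 91 days, and 91/112 = 81%.
- Exit on day 35: 112 − 35 = 77 days, and 77/112 = 69%.

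The window opens before the lower end of the one-to-two-month healing time that Section 5.1 cites from chinchillas.

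**2. False readings in an ear that stays open (assumed misread rate).** Let f be the chance that an open ear is read as healed at one look, with looks independent. Over the three scheduled looks (weeks 4, 10 and 16), the chance of at least one healed reading is 1 − (1 − f)³.

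| f per look | Recorded as healed at least once |
|---|---|
| 2% | 1 − 0.98³ = 5.9% |
| 5% | 1 − 0.95³ = 14.3% |
| 10% | 1 − 0.90³ = 27.1% |

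These figures apply only to ears that stay open. They are not the error in the overall healing proportion.

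**3. Net effect on the healing proportion (further assumptions).** Assume true healing of 30%, 50% and 60% by weeks 4, 10 and 16, a 95% chance that a closed ear is read as closed, every subject leaving at the first healed reading, and no reopening. A single week-16 reading for everyone gives 0.60 × 0.95 + 0.40 × f.

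| f per look | Exit at first healed reading | Week-16 reading for all | True |
|---|---|---|---|
| 2% | 61.8% (+1.8 points) | 57.8% (−2.2) | 60% |
| 5% | 65.2% (+5.2) | 59.0% (−1.0) | 60% |
| 10% | 70.4% (+10.4) | 61.0% (+1.0) | 60% |

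Across three assumed healing curves (true week-16 healing of 50% to 70%) and sensitivities of 90% to 100%, the net bias of the exit rule is +0.6 to +2.9 points at f = 2%, +3.1 to +7.1 at f = 5% and +7.1 to +13.5 at f = 10%. At f = 0 it is 0 to −1.7 points. At 90% sensitivity the break-even is near f = 1%.

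**4. Reopening after exit (assumed rates).** Overstatement = share exiting early × share of those that reopen.

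- 0.50 × 0.05 = 2.5 points, or 0.75 of 30 subjects.
- 0.50 × 0.20 = 10 points, or 3 of 30 subjects.

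**The case against.** The strongest reply is that the wording is permissive and the consequence limited. Exit on healing is allowed, not required, so a healed reading is final only for subjects who leave. The study is a small, descriptive safety study with no hypothesis, threshold or planned statistical analysis, and Section 5.1 does not claim durable closure. With 30 subjects, chance variation is wide in any case: the exact 95% interval around 18 of 30 is 41% to 77%. Photographs are taken at every visit, so a doubtful reading could be reviewed later without an amendment.

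Much of this stands. A reader might infer that every healed reading is final and every open reading can be reversed indefinitely. The protocol does not support that. After week 16, visits depend on visible device material or investigator discretion. The synopsis and Section 9 also allow exit once the device is gone, so an open ear may leave too and would stay a failure if it closed later. A reader might also count seven looks, to week 36, and arrive at much larger false-healing figures. Seven scheduled looks occur only if material stays visible into the extended visits, so three is the fair basis.

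Independence of misreads is doubtful as well. A thin or crusted membrane that misleads an investigator once may do so again. Correlation of that kind lowers the figures in step 2 and also lowers what confirmation can gain.

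The core survives. No section requires a confirming look, and none says which reading counts if a subject who stays is later read as open. Photographs may help with misreads, but they cannot show a reopening after the last visit. No later analysis can recover observations that were never made.

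**Conclusion.** The point holds as a cheap improvement. For subjects who exit on healing, the primary endpoint rests on one open-label, unconfirmed reading, and a later reopening is lost from both the healing table and the adverse event record. The only size fixed by the protocol is the 69% to 81% of the 16-week schedule left unobserved after exit at week 4.

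The size of the bias is unknown. From misreads alone it is upward unless false healed readings are rarer than roughly 1% per look, under the curves and sensitivities assumed above; any reopening after exit pushes it further up. It would be tempting to conclude that the healing rate is inflated by a known amount, or that a type I error is inflated. Neither follows: the protocol gives none of the rates needed, and it plans no test.

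**What to change.** **Exit rule.** In the synopsis, Section 4, Section 9, the notes to Sections 10.4, 10.5 and 10.8, and Appendix 1, remove study exit on healing before week 16. Subjects noted healed earlier then attend the week-10 and week-16 visits already in the schedule. In the same edit, make clear that exit because the device has cleared applies only to the extended visits, as Section 10.7 has it. Otherwise the wider wording in the synopsis and Section 9 could let early exit back in.

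**Endpoint.** In Section 5.1, report healing as closure present at week 16, and tabulate separately:

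- closed at two consecutive visits;
- closed once, not confirmed, including closure first seen at week 16 or later, with no visit added;
- closed, then reopened (an ear that reopens goes here whatever came before).

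**Cost.** A protocol amendment. A subject noted healed at week 4 attends two further planned visits, and one noted at week 10 attends one. Only a closure noted at an unscheduled visit before week 4 would mean more. No new procedure, reader or subjects are needed, and follow-up stays within the 16 weeks that Section 4 states. Adverse event collection for early healers extends to week 16 as a result. The reported healing proportion may be lower.

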10.5 Follow-up Evaluation - 10 weeks (\pm 7 days)

1. If applicable, record any new Adverse Events.
2. Record changes to concomitant medications.
3. Perform abbreviated physical examination.
4. Perform and record vital signs.
5. Otomicroscopy with photograph of tympanic membrane

Note: If complete healing is noted, then patient may exit the study and Subject Study CRF should be completed.

10.6 Follow-up Evaluation - 16 weeks (\pm 14 days) (and additional visits as applicable. See 10.7).

1. If applicable, record any new Adverse Events.
2. Record changes to concomitant medications.
3. Perform abbreviated physical examination.
4. Perform and record vital signs.
5. Otomicroscopy with photograph of tympanic membrane

Note: If complete healing is noted, then patient may exit the study and Subject Study CRF should be completed.

10.7 Potential Additional Follow-Ups at 20 weeks (\pm 14 days), 24 (\pm 14 days), 30 (\pm 14 days), 36 weeks (\pm 14 days) as needed.

It is expected that the Tympanoseal will have resorbed prior to 16 weeks. However, additional visits should be scheduled for 20 weeks, 24 weeks, 30 weeks and 36 weeks until no product remains. The subject may exit the study at any of these intervals after the device is no longer present.

1. If applicable, record any new Adverse Events.
2. Record changes to concomitant medications.
3. Perform abbreviated physical examination.
4. Perform and record vital signs.
5. Otomicroscopy with photograph of tympanic membrane

Note: If complete healing is noted, then patient may exit the study and Subject Study CRF should be completed.

Unscheduled Visit CRF pages will be used to capture 20, 24 and 30 week follow-ups, if needed.

10.8 Unscheduled Visit(s)

1. If applicable, record any new Adverse Events.
2. Record changes to concomitant medications.
3. Perform complete physical examination, record vital signs, and study evaluations.
4. Otomicroscopy with photograph of tympanic membrane
5. Please note the reason for the visit in the comments section.

Note: If complete healing is noted at this visit, the patient may exit the study and Subject Study CRF should be form completed.

11 ADVERSE EVENT REPORTING AND DOCUMENTATION

11.1 Adverse Events

An adverse event (AE) is any untoward medical occurrence in a clinical investigation of a medical device and that does not necessarily have a causal relationship with the treatment. An AE is therefore any unfavorable and unintended sign (including an abnormal laboratory finding), symptom or disease temporally associated with the administration of an investigational product, whether or not related to that investigational product.

The Investigator will determine with the subject, the occurrence of AEs during each subject visit and record the information in the site's source documents. Adverse events will be recorded in the patient CRF. Adverse events will be described by duration (start and stop dates and times), severity, outcome, treatment and relation to study device, or if unrelated, the cause.

AE Severity Grading

The guidelines below should be used to grade severity. It should be pointed out that the term "severe" is a measure of intensity and that a severe AE is not necessarily serious. (A 'severe' headache may not be a 'severe' AE.)

The collection period for all AEs will begin after device is implanted and ends at Subject Exit.

AE Severity Grading

Severity	Description
Mild (1)	Transient or mild discomfort; no limitation in activity; no medical intervention or therapy required. The subject may be aware of the sign or symptom but tolerates it reasonably well.
Moderate (2)	Mild to moderate limitation in activity, no or minimal medical intervention/therapy required.
Severe (3)	Marked limitation in activity, medical intervention/therapy required,, hospitalizations possible.
Life-threatening (4)	The subject is at risk of death due to the adverse experience as it occurred. This does not refer to an experience that hypothetically might have caused death if it were more severe.

AE Relationship to Study Device

The relationship of an AE to the study device should be assessed using the following the guidelines.

Relationship to Device	Comment
Definitely	Previously known toxicity of agent; or an event that follows a reasonable temporal sequence from use of the device; that follows a known or expected response pattern
Probably	An event that follows a reasonable temporal sequence from use of device; that follows a known or expected response pattern and that is unlikely to be explained by the known characteristics of the subject's clinical state or by other interventions.
Possibly	An event that follows a reasonable temporal sequence from use of the device; that follows a known or expected response; but that could readily have been produced by a number of other factors.
Unrelated	An event that can be determined with certainty to have no relationship to the study device.

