8.6 Instructions for Use

Operative Technique

This technique description is the suggested treatment for the uncomplicated procedure. The preferred treatment is that which addresses the needs of the specific patient. The perforation site is evaluated under the operating microscope and the edges of the perforation are manipulated with a small pick so as to freshen the margins of the perforation.

A perforation sizing device will be provided with each device which will allow the surgeon to estimate the diameter of a hole in the tympanic membrane in order to choose a repair construct of appropriate size.

The lyophilized device is provided in a protective capsule with four sizes each attached to the other with progressively smaller flanges along its length. The capsule is opened by bending the lateral tabs on its larger bottom portion with one hand while carefully removing the smaller top portion with the other hand. The device can be easily extracted with forceps.

The proper size for a given perforation is excised with surgical scissors or scalpel. One flange will be of a larger diameter than the other; the surgeon will implant the device with the larger flange laterally. Insertion of Tympanoseal is similar to the placement of a tympanostomy tube. Immediately after insertion normal saline should be instilled in the external auditory canal to swell the device and completely occlude the perforation.

After Tympanoseal is in place, wax earplugs should be in place during showers and swimming.

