14 STATISTICAL METHODS AND CONSIDERATIONS

As this study is for safety and utilizing a small number of subjects, no statistical analysis will be completed. Information will be presented to the FDA in tabular format.

Adverse event rates will be coded by body system will include the number of patients for whom the event occurred, the rate of occurrence, and the severity and relationship to study device.

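### Adverse events are rated for relationship to the device but not to the placement procedure, so ambiguous events after surgery cannot be told apart from device effects

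*Protocol*

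**What the plan says.** Section 11.1 of the protocol lists what is recorded for each adverse event: its duration and then "severity, outcome, treatment and relation to study device, or if unrelated, the cause". One causality scale follows, introduced by "The relationship of an AE to the study device should be assessed using the following the guidelines". It has four levels:

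- **Unrelated:** "An event that can be determined with certainty to have no relationship to the study device".
- **Possibly:** the event fits the timing and an expected response, "but that could readily have been produced by a number of other factors".
- **Probably:** the event is unlikely to be explained by the subject's "clinical state or by other interventions".
- **Definitely:** a previously known toxicity or, as an alternative, suitable timing together with a known or expected pattern.

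Section 9.1.7 gives the log entries: "severity/grade, outcome, treatment and relation to study device will be recorded on the Adverse Event Tracking Log". Neither a cause nor a relationship to the procedure is among them. Section 14 says that the safety table will give the number of patients with each event, "the rate of occurrence, and the severity and relationship to study device".

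Section 4 states that every subject has the device placed surgically, and section 8 that every subject receives it. In the technique suggested in section 8.6, "the edges of the perforation are manipulated with a small pick so as to freshen the margins of the perforation" before insertion. Under section 6.2, a retained tympanostomy tube is one of the two qualifying conditions.

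**The concern.** Safety is the primary objective (section 3.1). Surgery and device always come together, so no comparison between groups can separate harm from the surgical step from harm from the implant. That separation rests mainly on the causality judgement made for each event, and the form asks for only half of it. Hemorrhage and perforation enlargement are among the risks listed in section 2.1, and either could plausibly follow manipulation of the perforation edge as well as the presence of the implant.

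If the procedural contribution is not rated when the event occurs, it cannot be reliably recovered later. This is a data-collection item that the protocol itself fixes, so a later analysis plan cannot supply it. At stake is what the table sent to the FDA can support. Events in its device-related rows could be procedural, and a few true device reactions could go unnoticed among them.

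**Working it through.** The protocol gives no event rate, power or threshold bearing on this point, so there is no figure to reproduce. The check follows four kinds of event through the rules as written.

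| Event | Grade under 11.1 | Other cause requested? | What section 14 shows |
|---|---|---|---|
| A. Clearly procedural, device excluded with certainty | Unrelated | Yes in 11.1; not among the log items in 9.1.7 | Unrelated row, no cause |
| B. Soon after placement, could be surgery or device | Possibly or higher | No | Device-related row at that grade |
| C. True device reaction | Possibly to Definitely | No | Device-related row at that grade |
| D. Injury during the surgical step, before insertion | Outside the collection period in 11.1; inside it in 9.1.7 | Depends on which section governs | Absent under 11.1; under 9.1.7 handled as A, or as B if doubt remains |

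**Step 1, why B leaves the Unrelated row.** Unrelated needs certainty. Bleeding or pain that begins soon after the margin has been freshened and the implant inserted fits the timing of device use, and the device can rarely be excluded with certainty. The next level down in stringency is Possibly.

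**Step 2, what is lost there.** Possibly acknowledges that other factors may be responsible, but the record does not ask which. An event that surgery could explain and one that a concurrent illness could explain receive the same entry.

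**Step 3, whether B can go higher.** Probably is closed to an event that another intervention readily explains. The second limb of Definitely carries no such condition, only timing and an expected pattern. If the risks in section 2.1 count as expected responses, a surgical bleed could meet its literal wording.

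**Step 4, what the table can show.** B and C can share the same rows and no recorded item separates them. A has its own row, but its cause is not among the tabulated items.

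**Step 5, the collection window.** Section 11.1 starts collection once the implant is in place. Section 9.1.7 starts it on the procedure date. Under the first, D is missed. Under the second, D is captured without a procedure rating. Neither reading identifies procedural harm systematically.

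**The case against.** The strongest case on the other side has four parts.

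- **The scale already weighs other causes.** Probably and Possibly both do, and a clearly procedural event can be graded Unrelated with the procedure named. This stands. A reader might infer that every event is attributed to the device alone, and the text of 11.1 does not support that. The gap is confined to ambiguous events and to the cause that is not tabulated.
- **The table reports by relationship.** This also stands. A reader might infer that all procedural and device events are pooled, or that one device-related rate is inflated. Section 14 defines no rate that merges the grades. Suppose, purely as an assumption, that 1 of 30 subjects has a true device reaction and 0 to 4 others have procedural events graded Possibly or higher. A merged rate would then run from 1/30 = 3.3% to 5/30 = 16.7%. Those counts are invented and the merging is not planned. If the four were graded Possibly and the one Definitely, a table by grade would show them apart.
- **Other records exist.** Section 11.1 records start and stop dates and times and treatment. Section 10.2 adds a procedure and device form, and photographs are taken before and after placement. With at most 30 subjects, case review is feasible. It helps, but it is a retrospective substitute for a judgement the investigator could record at the time.
- **Counting ambiguous events as possibly device-related is conservative.** It is defensible in a small descriptive study with no test or stopping rule tied to the rate. A second rating keeps that caution and adds the missing information.

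Two further inferences go beyond the text. Section 8.6 calls its technique suggested, so margin freshening cannot be assumed at every placement. No share of subjects with a retained tube is given, so tube removal cannot be called frequent.

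**Conclusion.** The point holds for ambiguous events. Followed exactly, the protocol records no procedural attribution for an event that could come from either surgery or device, and section 14 does not carry forward the cause recorded for events graded Unrelated. In a study where all subjects have both surgery and device, such events cannot be separated from device effects within the device-related rows.

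The size cannot be derived from the document. It depends on how many ambiguous events occur and how they are graded, and neither is given. Any upward shift in the device-related rows is conditional on such events occurring after implantation, or on section 9.1.7 governing the collection window. Under 11.1, an injury before insertion would be missed rather than counted against the device.

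The conclusion assumes that investigators apply the certainty test for Unrelated literally. No planned test or decision rule is affected. This is an inexpensive improvement to what the main safety table can show.

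**What to change.** 1. In section 11.1 and on the Adverse Event Tracking Log (9.1.7), add for every adverse event a rating of relationship to the placement procedure, stated to include margin freshening and any tube removal, on the same four levels as the device scale.
2. In section 14, tabulate events as device-only, procedure-only, both and neither, by grade.
3. In the same edit, reconcile the start of event collection in 11.1 with that in 9.1.7, so that it is clear whether events during the surgical step before implantation are captured.

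The cost is one extra field per event and one extra table column. The second rating will not resolve every doubtful case. Some events will fall under both, but the table will then show that openly.
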